7.3. CRITERIA TO STOP TREATMENT

- 1. Failure to achieve CR/CRi/MLFS after 6 cycles of treatment, unless the patient is deemed to be deriving clinical benefit (e.g. blast reduction not meeting criteria for CR/CRi/MLFS) as assessed by the treating physician and PI
- 2. Unacceptable toxicity judged to be related to therapy by the investigator, as defined by the NCI Common Toxicity Criteria (irreversible or prolonged (> 42 days) grade 4 hematological toxicity or grade 4 non-hematological toxicity thought to be related to azacitidine, trametinib or venetoclax), unless it has been judged by the treating physician and PI that the patient is achieving clinical benefit.
- 3. Pattern of non-compliance by the patient with protocol requirements or patient's request to be removed from the study.
- 4. Relapse, defined as >5% bone marrow blasts not attributed to hematopoietic recovery, occurring after initial response to therapy
- 5. At the discretion of the treating physician and/or PI

Patients coming off treatment due to the above issues will continue to be followed for survival outcomes.

7.4 DEFINITION OF STUDY ENDPOINTS

- 1. Relapse-free survival is the time from documented CR/CRi until relapse or death.
- 2. Event-free survival is the time from the first day of treatment until any treatment failure (lack of response within 6 cycles of treatment, relapse, or death).
- 3. Overall response rate is defined as the percentage of patients achieving CR or CRi.
- **4. Overall survival** is defined as the time from the first day of treatment to time of death from any cause.

In the primary analysis, survival will not be censored for stem cell transplant.

8. REPORTING REQUIREMENTS

Adverse event reporting will be as per the NCI criteria and the MDACC Leukemia Specific Adverse Event Recording and Reporting Guidelines (refer to appendix E).

It is the responsibility of the PI and the research teams to ensure serious adverse events are reported according to the Code of Federal Regulations, Good Clinical Practices, the protocol guidelines, and Institutional Review Board (IRB) policy.

An adverse event is the appearance or worsening of any undesirable sign, symptom, or medical condition occurring after starting the study drug even if the event is not considered to be related to study drug. Medical conditions/diseases present before starting study drug are only considered adverse events if they worsen after starting study drug. Abnormal laboratory values or test results constitute adverse events only if they induce clinical signs or symptoms, are considered clinically significant, or require therapy.

The investigator (or physician designee) is responsible for verifying and providing source documentation for all adverse events and assigning the attribution for all adverse events for subjects enrolled.

The descriptions and grading scales found in the revised NCI Common Terminology Criteria for Adverse Events (CTCAE) version 5.0 will be utilized for adverse event reporting. (https://ctep.cancer.gov/protocoldevelopment/electronic_applications/ctc.htm#ctc_50).

9. OUTSIDE PHYSICIAN PARTICIPATION DURING TREATMENT

- 9.1 MDACC Physician communication with the outside physician is required prior to the patient returning to the local physician. This will be documented in the patient record.
- 9.2 A letter to the local physician outlining the patient's participation in a clinical trial will request local physician agreement to supervise the patient's care

- 9.3 Protocol required evaluations outside MDACC will be documented by telephone, fax or email. Fax and/or e-mail will be reviewed by the MDACC physician and any additional medical intervention is required it will be documented within the patient's medical record
- 9.4 Changes in drug dose and/or schedule must be discussed with and approved by the MDACC physician investigator, or their representative prior to initiation, and will be documented in the patient's medical record.
- 9.5 A copy of the informed consent, treatment schema and evaluation during treatment will be provided to the local physician.
- 9.6 Documentation to be provided by the local physician will include drug administration records, progress notes, reports of protocol required laboratory and diagnostic studies and documentation of any hospitalizations.
- 9.7 The home physician will be requested to report to the MDACC physician investigator all life threatening events within 24 hours of documented occurrence.
- 9.8 For non MD Anderson laboratory results, the principal investigator (or physician designee) will review laboratory results, determine clinical significance, and sign and date the results.

10. STATISTICAL METHODOLOGY

This is an open label, phase II study with a lead-in phase to assess the MTD and the efficacy of the combination regimen of azacitidine, venetoclax, and trametinib in patients with AML or MDS/CMML. A total of 40 patients will be enrolled for the study: 20 patients with newly diagnosed AML (Cohort A) and 20 patients with relapsed/refractory AML or higher-risk MDS or CMML (Cohort B).

In order to confirm the safety of azacitidine, venetoclax, and trametinib, there will be a lead-in phase for the regimen safety. The regimen will initially be explored in 6 eligible patients meeting criteria for enrollment in Cohort B (i.e. relapsed/refractory). If none or only one of the 6 patients experiences DLT in first cycle attributable to the treatment components, the phase II portion of the study will proceed as detailed below. The patients treated in this confirmatory phase will be counted towards the phase II component of the study. If DLT attributable to the components is observed in 2 or more of these initial 6 patients, accrual to the phase II portion of the study will be deferred, and a lower dose of the combined agents would be assessed based on the investigators' decision, which will be implemented with amendment to the study.

Cohort A:

The historical 1-year overall survival rate (OSR) for newly diagnosed patients is 59% and for this cohort the target OSR is 65% for the experimental treatment. A >30% clinically significant drug-related grade 3 or higher toxicity rate occurred in the 1st cycle is considered unacceptable. A sample size of 20 patients ensures that, if the cohort is not terminated early, a posterior 95% credible interval for OSR will be (0.38, 0.78) under the assumption of a 59% of OSR and prior Beta (1.18, 0.82). Thus, interim monitoring rules, assuming the prior distributions below, were constructed that meet the following two conditions,

- 1) Stop if Prob[p(OSR, H) + δ_{OSR} > P(OSR, E) | data] > 0.95, where δ_{OSR} = 0.06 or
- 2) Stop if Prob[p(TOX,H) + δ_{TOX} < p(TOX,E)| data] > 0.90, where δ_{TOX} = 0,

where p(OSR, H) and p(OSR, E) are the true OSR for the historical and experimental treatments, respectively. The p(TOX, H), and p(TOX, E) are the toxicity rates for the historical and experimental treatments, respectively. The first rule provides for stopping the study if the data suggest that it is unlikely (i.e., probability < 5%) that OSR rate of the regimen is greater than 65%. The second condition will stop the study early if excessive therapy-related grade 3 or higher toxicity (>30%) is highly probable (i.e., probability >90%) for the combination treatment. Monitoring for toxicity and futility will not begin until 4 patients have been evaluated, and cohort size for future evaluations is 4.

The monitoring rule for the toxicity and OSR rates, based on these assumptions and monitoring conditions above is found in Table 1. For example, accrual will cease if 3 or more patients experience toxicities among the first 4 patients. Accrual will cease if none of first 4 patients treated are alive.

Table 1. Stopping boundary for efficacy and toxicity				
# patients	Stop the cohort if there are	ort if there are this number of patients		
evaluated	# alive	with toxicities		
4	0	3-4		
8	0-2	5-8		
12	0-4	6-12		
16	0-7	8-16		
20	Stop due to maximum sample size	Stop due to maximum sample size		

Table 2 shows the operating characteristics for simultaneous monitoring response and toxicity rates. The probability of stopping the study early if the true OSR rate of the combination treatment was 65% and the true toxicity rate was 30% was 25%. Probabilities of stopping early for high true toxicity rates (i.e., 50%) were 74% when the true OSR was 65%.

Table 2. Operating characteristics	Table 2. Operating characteristics for simultaneous monitoring response and toxicity rates			
True Toxicity Rate	True OSR	Prob(stop the cohort early)		
0.20	0.55	0.3163		
	0.60	0.2037		
	0.65	0.1255		
	0.70	0.0793		
	0.75	0.0566		
0.30	0.55	0.4135		
	0.60	0.3169		
	0.65	0.2498		
	0.70	0.2102		
	0.75	0.1907		
0.40	0.55	0.5940		
	0.60	0.5271		
	0.65	0.4806		
	0.70	0.4532		
	0.75	0.4397		
0.50	0.55	0.7956		

Table 2. Operating characteristics for simultaneous monitoring response and toxicity rates			
True Toxicity Rate True OSR Prob(stop the cohort early)			
	0.60	0.7619	
	0.65	0.7386	
	0.70	0.7247	
	0.75	0.7179	

Multc Lean Desktop (version 2.1.0) was used to generate the toxicity and futility stopping boundaries and the operating characteristics table. In order to utilize the software for the design, a 59% constant rate, a 6% delta and beta (1.18, 0.82) priors were assumed for the standard treatment response rate and experimental treatment response prior distribution, respectively. In addition, a 30% constant rate and beta (0.6, 1.4) priors were assumed for the standard treatment toxicity rate and experimental treatment toxicity prior distribution, respectively.

Cohort B:

The target CR/CRi/MLFS rate is 35% evaluated within 6 cycles of treatment. A >30% clinically significant drug-related grade 3 or higher toxicity rate occurred in the 1st cycle is considered unacceptable. A sample size of 20 patients ensures that, if the cohort is not terminated early, a posterior 95% credible interval for CR/CRi/MLFS will be (0.17, 0.56) under the assumption of a 35% of CR/CRi/MLFS and prior Beta (0.7, 1.3). Thus, interim monitoring rules, assuming the prior distributions below, were constructed that meet the following two conditions,

- 1) Stop if Prob[p(CR/CRi, E) < 0.35 | data] > 0.95, or
- 2) Stop if Prob[p(TOX, E) > 0.30 | data] >0.93,

where p(CR/CRi/MLFS, E) and p(TOX, E) are the true CR/CRi/MLFS and toxicity rates for the regimen. The first rule provides for stopping the study if the data suggest that it is unlikely (i.e., probability < 5%) that CR/CRi/MLFS rate of the regimen is greater than 35%. The second condition will stop the study early if excessive therapy-related grade 3 or higher toxicity (>30%) is highly probable (i.e., probability >93%) for the combination treatment. Monitoring for toxicity and futility will not begin until 4 patients have been evaluated, and cohort size for future evaluations is 4.

The monitoring rule for the toxicity and CR/CRi/MLFS rates, based on these assumptions and monitoring conditions above is found in Table 3. For example, accrual will cease if 3 or more patients experience toxicities among the first 4 patients. Accrual will cease if no patient experience an overall response in the first 8 patients treated.

Table 3. stopping boundary for efficacy and toxicity				
# patients avaluated	Stop the cohort if there are	this number of patients		
# patients evaluated	<pre># patients with CR/CRi/MLFS</pre>	# patients with toxicities		
4	Never stop	3-4		
8	0	5-8		

12	0-1	7-12
16	0-2	8-16
20	Stop due to maximum sample size	Stop due to maximum sample size

Table 4 shows the operating characteristics for simultaneous monitoring response and toxicity rates. The probability of stopping the study early if the true CR/CRi/MLFS of the combination treatment was 35% and the true toxicity rate was 30% was 21%. Probabilities of stopping early for high true toxicity rates (i.e., 50%) were 75% when the true CR/CRi/MLFS was 35%.

Table 4. Operating characteris	tics for simultaneous monitoring	response and toxicity rates
True Toxicity Rate	True CR/CRi/MLFS	Prob(stop the cohort early)
0.20	0.25	0.2785
	0.30	0.1728
	0.35	0.1076
	0.40	0.0709
	0.45	0.0519
0.30	0.25	0.3628
	0.30	0.2694
	0.35	0.2118
	0.40	0.1794
	0.45	0.1626
0.40	0.25	0.5372
	0.30	0.4695
	0.35	0.4276
	0.40	0.4041
	0.45	0.3919
0.50	0.25	0.7544
	0.30	0.7184
	0.35	0.6962
	0.40	0.6837
	0.45	0.6772

Multc Lean Desktop (version 2.1.0) was used to generate the toxicity and futility stopping boundaries and the operating characteristics table. In order to utilize the software for the design, a 35% constant rate and beta (0.7, 1.3) priors were assumed for the standard treatment response rate and experimental treatment response prior distribution, respectively. In addition, a 30% constant rate and beta (0.6, 1.4) priors were assumed for the standard treatmental treatment toxicity prior distribution, respectively.

Analysis Plan: Demographic/clinical characteristics and safety data of the patients will be summarized using descriptive statistics such as mean, standard deviation, median and range.

For the primary efficacy analysis, we will estimate the CR/CRi/MLFS for the combination treatment (defined as the proportion of patients achieving CR or CRi or MLFS within 6 cycles of treatment), along with the 95% credible interval. This regimen will be considered worthy of further investigation if a CR/CRi/MLFS rate of at least 35% is achieved for frontline patients (Cohort B). Other efficacy endpoints (e.g. CR rate, CR/CRi rate, minimal residual disease negativity, or proportion of patients proceeding to HSCT) will also be estimated along with 95% credible intervals. The association between response and patient's clinical characteristics (e.g., baseline apoptotic protein levels, baseline FLT3 allelic ratio, or baseline genomic alterations) will be examined by Wilcoxon's rank sum test or Fisher's exact test, as appropriate.

For each subject, relapse-free survival (RFS), event-free survival (EFS) and overall survival (OS) will be calculated. The distribution of time-to-event endpoints (OS, EFS and OS) will be estimated using the method of Kaplan and Meier. Comparisons of time-to-event endpoints by important subgroups (e.g., baseline genomic alterations will be made using the log-rank tests.

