2. STUDY OBJECTIVES AND ENDPOINTS

2.1. Primary Objectives

- Cohort A: To determine overall survival rate at 1 year of the regimen in patients with newly diagnosed AML
- Cohort B: To determine the complete remission(CR)/Complete remission without recovery of counts (CRi)/morphologic leukemia-free state (MLFS) rate of the regimen in patients with relapsed/refractory AML or high-risk MDS

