6.5 Long-Term Follow-up

After discontinuing study treatment (unless discontinuing due to withdrawal of consent) patients will be followed for disease progression, relapse, and survival. Patients will be followed for survival every 6 months (±3 months) until death via brief phone call, even after being taken off treatment. For patients registered on our long-term follow-up umbrella protocol DR09-0223, survival follow-up may be conducted under that protocol.

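### Cohort A futility rule: Table 2's early-stopping probabilities hold only if each counted patient's 12-month status is known before accrual continues, and the plan does not secure this

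*Combined protocol and SAP*

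**What the plan says.** Section 2.1 sets the Cohort A primary objective: "To determine overall survival rate at 1 year of the regimen in patients with newly diagnosed AML". Section 10 builds the design on the same quantity: "The historical 1-year overall survival rate (OSR) for newly diagnosed patients is 59" percent, with a target of 65%. The futility condition is set on this rate, and section 10 presents Table 1 as the monitoring rule for OSR and toxicity.

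Table 1 gives one column of patients evaluated (4, 8, 12, 16), a survival boundary headed only *# alive* (0, 0-2, 0-4, 0-7) and a toxicity boundary. The worked example is "Accrual will cease if none of first 4 patients treated are alive". On timing, section 10 says: "Monitoring for toxicity and futility will not begin until 4 patients have been evaluated, and cohort size for future evaluations is 4". It does not define evaluated for survival.

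Elsewhere:
- Section 7.4 says that overall survival "is defined as the time from the first day of treatment to time of death from any cause". It defines no 12-month status.
- Section 6.5, for patients off study treatment: "Patients will be followed for survival every 6 months (±3 months) until death via brief phone call". These contacts are not linked to the monitoring looks.
- Toxicity is dated to the first cycle. Cohort B response is dated as well: "The target CR/CRi/MLFS rate is 35% evaluated within 6 cycles of treatment".

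The documents give no accrual rate for Cohort A, no pause in accrual before a look, and no rule for counting a patient who is alive with less than 12 months of follow-up.

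**The concern.** A futility rule on a 12-month endpoint can halt accrual only if the 12-month results arrive while there are still patients to enrol. Table 2 is computed as if each block of four had complete survival results before the next block entered. If patients keep entering while status is awaited, a boundary may be crossed when the cohort is already full, and the instruction to cease accrual then has nothing to act on.

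At stake is the protection that Table 2 promises when survival is poor. A reader takes from the table that a regimen with a true OSR of 55% has a stated chance of being stopped early. In practice that chance could be much smaller, and the monitoring committee has no written rule on when to read survival or how to count patients with short follow-up.

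**Working it through.** **Inputs from section 10.** Futility: stop if P(p < 0.65 | data) > 0.95, where 0.65 = 0.59 + 0.06, with prior Beta(1.18, 0.82). Toxicity: stop if P(p > 0.30 | data) > 0.90, with prior Beta(0.6, 1.4). Looks at 4, 8, 12 and 16; maximum 20.

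**1. Table 1 reproduces.** With s alive of n, the posterior is Beta(1.18 + s, 0.82 + n − s). P(p < 0.65) at the boundary and one patient above it:

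| n | At boundary | One above |
|---|---|---|
| 4 | s = 0: 0.991 | s = 1: 0.926 |
| 8 | s = 2: 0.985 | s = 3: 0.932 |
| 12 | s = 4: 0.984 | s = 5: 0.943 |
| 16 | s = 7: 0.954 | s = 8: 0.884 |

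The same method gives toxicity limits of 3, 5, 6 and 8, as printed.

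**2. Table 2 reproduces.** An exact recursion over blocks of four, with complete binary outcomes, gives futility-only stopping F = 0.2850 at OSR 0.55 and 0.0854 at OSR 0.65, and toxicity-only stopping T = 0.0439 at 0.20 and 0.1798 at 0.30. The combined value is 1 − (1 − F)(1 − T). For toxicity 0.30 and OSR 0.65: 1 − 0.9146 × 0.8202 = 0.2498, as printed. All 20 cells match to four decimals.

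**3. When the looks fall if accrual does not pause.** Let r be patients per month (assumed; the documents give none), with evenly spaced entry.
- Patient n reaches 12 months at (n − 1)/r + 12. Patient 20 enters at 19/r.
- Look n comes before patient 20 enters only if r < (20 − n)/12. The limits are 1.33 (n = 4), 1.00 (n = 8), 0.67 (n = 12) and 0.33 (n = 16).
- Patients enrolled when patient 4 reaches 12 months: 4 + 12r, which is 7, 10 and 16 at r = 0.25, 0.5 and 1, and all 20 at r = 2.
- At r = 0.25 all four looks are in time, so nothing is lost. At 0.5 the first three are in time, and futility stopping at OSR 55% is 0.155. At 1 only the first is in time: 0.45⁴ = 0.041. At 2 none is.

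**4. Poisson accrual, exponential survival, no pause.** Simulation with 200,000 trials per cell. Stop means before patient 20 enters; look n is taken 12 months after entry n. Futility only:

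| OSR | Design | r = 0.25 | 0.5 | 1 | 2 |
|---|---|---|---|---|---|
| 55% | 0.285 | 0.24 | 0.16 | 0.07 | 0.002 |
| 65% | 0.085 | 0.07 | 0.05 | 0.02 | 0.001 |

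If each look is instead taken as soon as all n patients have died or reached 12 months, the OSR 55% row becomes 0.26, 0.19, 0.10 and 0.02. With Weibull shapes from 0.6 to 1.3 at r = 0.5, the tabulated 0.16 does not change.

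**5. Stopping as soon as a boundary is certain.** If a is the Table 1 survival boundary, n − a deaths within 12 months among the first n settle the look: 4 − 0 = 4, 8 − 2 = 6, 12 − 4 = 8, 16 − 7 = 9. Under the assumptions of step 4, this gives 0.28, 0.24, 0.15 and 0.04 at OSR 55%, and 0.08, 0.07, 0.045 and 0.01 at OSR 65%.

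**The case against.** The strongest reply is that section 10 already supplies the time point. It defines OSR as the 1-year rate and presents Table 1 as the rule for OSR, so *# alive* is the count of 12-month survivors. On that reading the probability of crossing a boundary equals the Table 2 figure at any accrual rate. The shortfall appears only when stopping is taken to mean stopping before patient 20 enters, and its size rests on an accrual rate that the documents do not give. Toxicity monitoring, dated to cycle 1, supplies about 0.18 of the 0.25 at toxicity 30% and OSR 65%. The cohort has 20 patients, and section 12 names a monitoring committee.

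Most of this stands. The column label is a clarification, Table 2 is not miscalculated, and no single effect size can be drawn from the documents. But the stated action is to cease accrual, so a crossing found after the last patient has entered does not deliver what Table 2 describes. Committee oversight does not supply the missing rule either.

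A reader might go further and take *# alive* literally, as alive on the date of the look, so that deaths after month 12 count and a regimen on target could be stopped too often. If status is read when the nth patient completes cycle 1, simulation gives 0.65 at OSR 65% with 0.25 patients per month. The documents do not support this as the intended rule, because such a count does not estimate the 1-year rate on which the futility condition is set. Over-stopping also needs slow accrual: 0.25 per month means about 20/0.25 = 80 months to enrol, and at 1 per month the same reading gives 0.01, below the design's 0.085. It is a secondary risk that a clear label removes.

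**Conclusion.** The point holds, and the plan should be amended. Tables 1 and 2 are correct as computed, and alive at 12 months is the natural meaning. What is not secured is the condition behind Table 2. If accrual continues while status is awaited, the chance of stopping before patient 20 enters is generally below the stated value when survival is poor: at OSR 55%, between 0.24 and 0.002 for Poisson accrual of 0.25 to 2 per month, against 0.285 for futility alone. Evenly spaced entry at 0.25 per month shows no loss.

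The boundary-crossing probability, toxicity stopping and the final 1-year survival estimate are not affected. It would be too strong to infer that Table 2 is wrong, or that the trial would stop a good regimen too often. Confidence is high that Table 2's probabilities are not secured, and moderate on the size, which rests on assumed accrual and survival curves.

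**What to change.** 1. Label the Table 1 survival column as alive at 12 months from the first day of treatment, so that later deaths do not count.
2. Take toxicity looks when patients 4, 8, 12 and 16 complete cycle 1, and run survival looks separately. Update vital status for all Cohort A patients before each survival decision, because routine off-treatment contact is too sparse for this purpose.
3. Keep Table 1, and cease accrual as soon as deaths within 12 months make a boundary certain: 4 of the first 4, 6 of the first 8, 8 of the first 12, or 9 of the first 16. This needs the same boundary crossing, so it cannot stop more often than the design.
4. State the expected accrual rate and restate Table 2 under this rule. With toxicity stopping as designed and r = 0.5 and 1 per month:
   - Toxicity 0.20, OSR 0.55: from 0.316 to 1 − 0.759 × 0.9561 = 0.27 and 1 − 0.846 × 0.9561 = 0.19.
   - Toxicity 0.30, OSR 0.65: from 0.250 to 1 − 0.929 × 0.8202 = 0.24 and 1 − 0.955 × 0.8202 = 0.22.

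The cost is a few sentences and one re-simulation. Sample size, priors and boundaries do not change. The downside is a less favourable stated stopping probability: the rule recovers part of the loss (at OSR 55%, from 0.16 to 0.24 at 0.5 per month and from 0.07 to 0.15 at 1 per month) and little at 2 per month. An accrual pause at each look, or a time-to-event monitoring rule, is an optional trade-off and not part of this fix.

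### Cohort B: the text gives a 75% chance of stopping early at 50% toxicity and 35% response, but Table 4 and the Table 3 boundaries give 69.6%

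*Combined protocol and SAP*

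**What the plan says.** Section 10 gives Cohort B two stopping rules, checked after every 4 evaluated patients. The futility rule is "Stop if Prob[p(CR/CRi, E) < 0.35 | data] > 0.95, or" and the toxicity rule is "Stop if Prob[p(TOX, E) > 0.30 | data] >0.93". Table 3 turns these into counts, and Table 4 lists the probability of stopping early for 20 combinations of true toxicity and true response.

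The text introducing Table 4 summarises two of those combinations. For the first, the stopping probability when CR/CRi/MLFS "was 35% and the true toxicity rate was 30% was 21" per cent. For the second: "Probabilities of stopping early for high true toxicity rates (i.e., 50%) were 75% when the true CR/CRi/MLFS was 35" per cent.

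The Cohort A text does the same for Table 2. The stopping probability when the one-year survival rate "was 65% and the true toxicity rate was 30% was 25" per cent, and then "Probabilities of stopping early for high true toxicity rates (i.e., 50%) were 74% when the true OSR was 65" per cent.

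**The concern.** The second Cohort B sentence disagrees with the table it describes. Table 4 has 0.6962 at toxicity 0.50 and response 0.35, which rounds to 70%. A gap of 5.4 points is not rounding.

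The sentence matters because it is the protocol's only statement in words of how often the Cohort B rules stop a clearly too toxic regimen when response is at target; Section 10 treats toxicity above 30% as unacceptable. The error is in the reassuring direction. It also makes the two cohorts look equally protected at their target rates (75% and 74%), when the tables show Cohort B's rules to be somewhat weaker (69.6% against 73.9%).

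**Working it through.** **Inputs (all from Section 10, Cohort B)**
- Looks at 4, 8, 12 and 16 evaluated patients. At 20 the cohort ends because it is full, so that is not an early stop.
- Response prior Beta(0.7, 1.3), reference 0.35, cut-off 0.95.
- Toxicity prior Beta(0.6, 1.4), reference 0.30, cut-off 0.93.
- Assumption: response and toxicity are independent. Reproducing Table 4 bears this out.

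**Step 1: do the rules give the Table 3 boundaries?** With x events in n patients, the posteriors are Beta(0.7 + x, 1.3 + n − x) for response and Beta(0.6 + x, 1.4 + n − x) for toxicity. Futility stops at the largest x with P(p < 0.35) > 0.95. Toxicity stops at the smallest x with P(p > 0.30) > 0.93.

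| n | Futility: stop at or below | Posterior there | Toxicity: stop at or above | Posterior there |
|---|---|---|---|---|
| 4 | never (0 responses gives 0.940) | – | 3 | 0.935 |
| 8 | 0 | 0.991 | 5 | 0.954 |
| 12 | 1 | 0.983 | 7 | 0.969 |
| 16 | 2 | 0.979 | 8 | 0.940 |

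These are exactly the Table 3 boundaries.

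**Step 2: probability of stopping.** For each endpoint, carry the binomial distribution of the running count forward 4 patients at a time, removing the paths that reach the boundary. Then

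P(stop early) = 1 − P(no toxicity stop) × P(no futility stop).

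Toxicity rule alone at 50% toxicity, by look:

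0.3125 + 0.1328 + 0.0774 + 0.1492 = 0.6719, so P(no toxicity stop) = 0.3281.

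Futility rule alone, by look (8, 12, 16):
- at 35% response: 0.0319 + 0.0245 + 0.0177 = 0.0740 (unrounded sum), so P(no futility stop) = 0.9260;
- at 25% response: 0.1001 + 0.0845 + 0.0668 = 0.2514, so P(no futility stop) = 0.7486.

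Combined at 50% toxicity:
- 35% response: 1 − 0.3281 × 0.9260 = **0.6962**
- 25% response: 1 − 0.3281 × 0.7486 = **0.7544**

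All 20 Table 4 entries are reproduced to four decimals. The same method with the Table 1 boundaries reproduces all 20 Table 2 entries.

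**Step 3: compare the four summary figures with their tables.**

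| Cohort | True toxicity | True response or survival | Text | Table | Agrees |
|---|---|---|---|---|---|
| A | 0.30 | 0.65 | 25% | 0.2498 | yes |
| A | 0.50 | 0.65 | 74% | 0.7386 | yes |
| B | 0.30 | 0.35 | 21% | 0.2118 | yes |
| B | 0.50 | 0.35 | 75% | 0.6962 | **no** |

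Only one Table 4 entry rounds to 75%: 0.7544, at toxicity 0.50 and response 0.25.

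**Step 4: could another reading give 75% at (0.50, 0.35)?**
- Cohort A's toxicity cut-off of 0.90 (boundary 6 instead of 7 at 12 patients): 73.5%. This contradicts Table 3 and would turn the matching 21% into 24%.
- Toxicity cut-off 0.95: 56.2%.
- Counting a look at 20 patients as an early stop: 74.2%.
- Extreme positive or negative dependence between response and toxicity (simulated): about 73.0% or 67.4%.

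None rounds to 75%.

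**The case against.** The practical effect is very small. The correct value is printed in the table that the sentence introduces, and no boundary, decision rule or analysis uses the 75%. That stands, and it is why the point is minor.

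Three limits on what may be claimed also stand.

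- **Cause.** A misread row is an inference. A typing slip or a leftover from another design cannot be ruled out. The error does not depend on its cause.
- **Meaning of the 30%.** The non-stopping probability of 0.304 belongs to the Table 3 rules alone and refers to patients evaluated. Section 10 does not say that accrual pauses while responses within 6 cycles are awaited, so it is not a statement about how many patients will have been enrolled.
- **The lead-in.** Two or more DLTs in the first 6 relapsed/refractory patients defer accrual, and "The patients treated in this confirmatory phase will be counted towards the phase II component of the study". Overall protection is therefore somewhat greater than Table 4 shows. How much depends on the share of counted toxicities that are DLTs, which the documents do not give. If DLTs are a subset of the counted toxicities, the stop-or-defer probability at 50% toxicity and 35% response is 0.72, 0.77 or 0.91 for assumed shares of 25%, 50% or 100%.

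A share between 25% and 50% would give about 75%, but this does not rescue the sentence. The sentence describes Table 4, which leaves the lead-in out, and its companion figure of 21% is the Table 4 value. With the lead-in included, the companion would be 25%, 34% or 61% at those three shares.

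**Conclusion.** The concern holds. The stated 75% should be 69.6%, or 70% rounded, an overstatement of 75.0 − 69.6 = 5.4 points. Under the Table 3 rules alone, a Cohort B regimen with 50% toxicity and 35% response goes without an early stop with probability 1 − 0.6962 = 0.304, rather than the 0.25 that the text implies. Tables 3 and 4 are correct and consistent with the stated priors and cut-offs. The figure rests on the boundaries as printed and on independence of response and toxicity, the assumption under which all 20 table entries are reproduced. Severity: minor.

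**What to change.** In the Cohort B text introducing Table 4, change 75% to 70% (0.6962). This is one number in one sentence. It needs no new simulation and changes no boundary, sample size or conduct. The only consequence is that the stated stopping probability becomes about 5 points lower.

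Optionally, and separately from the correction, add one sentence saying that Table 4 covers the Table 3 monitoring rules only and leaves out the lead-in deferral rule. No combined probability should be quoted unless the assumed DLT share is stated with it.
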